2.1 Data analysis general information

This study will be conducted under the sponsorship of Novartis.

The analysis outlined in this document will be performed by Novartis or a designated contract research organization (CRO) (if applicable). SAS® version 9.4 or higher will be used for generating tables, figures, and listings (TFLs). It is planned that the data from all participating centers will be used.

Data will be listed for all patients with respect to demographic and baseline characteristics, efficacy, and safety observations and measurements.

All data will be listed by center, patient number and one treatment arm of the tisagenlecleucel (tisagenlecleucel is as defined in [Section 2.1.1.1](#)), unless stated otherwise.

2.1.1 General definitions

2.1.1.1 Tisagenlecleucel re-infusion

A second dose of commercial tisagenlecleucel is not considered study treatment because it is released commercially to the treating physician when it is prescribed in the course of medical practice. The doses available for re-infusion were previously manufactured for each individual patient as commercial product and a physician can request an additional dose for commercial release at any time, prior to product expiration and subject to availability.

2.1.1.2 Date of re-infusion of tisagenlecleucel

The date of re-infusion of tisagenlecleucel is defined as the date when a non-zero dose of tisagenlecleucel was administered and recorded on the “Dosage Administration Record - IV - Tisagenlecleucel T-Cell Infusion (Second Infusion)” electronic Case Report Form (eCRF). A single re-infusion is planned. Note that re-infusion refers to the **second** infusion of tisagenlecleucel. This study will follow the patient journey post re-infusion.

2.1.1.3 Date of infusion of tisagenlecleucel

Note that prior to study enrollment into this re-infusion study, patients will have a date for their first tisagenlecleucel infusion. The date of first infusion is recorded on the “Dosage Administration Record - IV - Tisagenlecleucel T-Cell Infusion (First Infusion)” eCRF.

2.1.1.4 Date of first administration of lymphodepleting chemotherapy

The date of first administration of lymphodepleting chemotherapy is defined as the first date when a non-zero dose of lymphodepleting chemotherapy was administered and recorded on the “Bridging or Lymphodepleting Chemotherapy-Medication” eCRF for the indication “Lymphodepleting chemotherapy”.

2.1.1.5 Date of first administration of bridging therapy

The date of first administration of bridging therapy is defined as the first date when a non-zero dose of bridging therapy was administered and recorded on the “Bridging or Lymphodepleting Chemotherapy-Medication” eCRF for the indication “Bridging therapy”.

2.1.1.6 Date of first treatment

For patients who received lymphodepleting chemotherapy and/or bridging therapy prior to re-infusion, the date of first treatment is the date of first administration of lymphodepleting chemotherapy or bridging therapy. For patients who did not receive lymphodepleting chemotherapy or bridging therapy, the date of first treatment is the date of re-infusion of tisagenlecleucel.

2.1.1.7 Study day

The study day will be calculated as the difference between the date of the assessment and the date of re-infusion of tisagenlecleucel (defined as **Study Day 1**) plus 1 day for assessments on or after the date of re-infusion. Duration of an event will be calculated as:

- Duration of event = (Event end date – Event start date) + 1 (in days)

For assessments before the date of re-infusion, the study day will be calculated as the difference between the date of the assessment and **Study Day 1** (*Note: if an event happens before Study Day 1 then the study day will be negative*).

For patients who do not receive tisagenlecleucel in this study, their study days will not be calculated.

For the partial date study day will not be calculated.

The study days will be displayed in all relevant data listings.

2.1.1.8 Baseline assessments

Not applicable.

2.1.1.9 Last contact date

Not applicable.

2.1.1.10 Time-to-event

Not applicable.

2.1.1.11 Percent change from baseline

Not applicable.

2.2 Analysis sets

Screened Set: The Screened Set comprises all patients who have signed informed consent/assent and been screened in the study.

Enrolled Set: The Enrolled Set (ENS) comprises all patients who are enrolled in the study. Enrollment is defined as the point at which the patient meets all inclusion/exclusion criteria and the patients' additional non-expired dose of tisagenlecleucel has been confirmed available.

Full Analysis Set: The FAS consists of all patients who have received re-infusion of tisagenlecleucel.

Safety Set: The Safety Set consists of all patients who have received re-infusion of tisagenlecleucel.

2.3 Patient disposition, demographics and other baseline characteristics

All baseline disease characteristics and demographics will be listed from Enrolled Set, unless stated otherwise.

No inferential tests for differences in background and demographic characteristics will be performed.

2.3.1 Patient disposition

The patient disposition for each phase will be listed for the Screened Set for all patients who entered the study. Patients who have entered any study phase but have discontinued from the study will be listed as appropriate along with the primary reason for discontinuation.

2.3.2 Demographics

The following demographic data will be listed:

Note: Dependent on when the COVID-19 pandemic may end versus when patients are enrolled in this study, the listing may be given by pandemic impact.

- Age at Screening (years)
Age at Screening stratification category (<10 years, ≥ 10 to < 18 years, ≥ 18 years)
- Sex (Male, Female, Unknown, Undifferentiated)
- Weight (kg)
- Height (cm)
- Body mass index (BMI) (kg/m²)
 - Defined as: (weight in kg) / (height in meters)²
- Race (White, Black or African American, Asian, Native Hawaiian or Other Pacific Islander, American Indian or Alaska Native)
- Ethnicity (Hispanic or Latino, Not Hispanic or Latino, Not reported, Unknown)

- Karnofsky/Lansky performance status (100, 90, 80, 70, 60, 60, <50)

2.3.3 Baseline characteristics

2.3.3.1 Primary disease history

The following primary disease history will be listed:

Note: Dependent on when the COVID-19 pandemic may end versus when patients are enrolled in this study, the listing may be given by pandemic impact.

- Age at initial diagnosis (years)
- WBC at initial diagnosis ($\geq 50 \times 10^9$ cells/L, $< 50 \times 10^9$ cells/L)
- Date of initial diagnosis of ALL (years)
- Date of first tisagenlecleucel infusion (months)
- Date of loss of B-cell aplasia following first tisagenlecleucel infusion (months)

Note: Date of loss of B-cell aplasia is equivalent to date of study enrollment.

2.3.3.2 ALL characteristics

The following ALL disease characteristics at Baseline will be listed

- Evidence of extramedullary involvement (Yes, No)
- CD19 status (Positive, Negative, Not Done, Unknown)
- Overall minimal residual disease (MRD) status (Positive, Negative, Not Done, Unknown)
- MRD biomarker analyte and associated phenotype result (%)

2.3.3.3 Medical history

Medical history and ongoing conditions at Baseline will be listed.

Note: If there are COVID-19 infected patients in this study, listing of medical history will be provided first by all patients of interest, then by COVID-19 infected patients and non-COVID-19 infected patients.

Medical histories will be coded using the Medical Dictionary for Regulatory Activities (MedDRA) terminology version 24.1 or higher. The primary SOCs will be presented in alphabetical order. Preferred terms will be sorted by decreasing proportion and alphabetical order.

2.3.3.4 ALL prognostic factors

The qualitative ALL prognostic factors as captured on the “Prognostic factors” eCRF and will be listed.

- Age (≤ 12 years, > 12 years, Unknown)
- Elevated lactate dehydrogenase (LDH) $>$ upper limit of normal (Yes, No, Unknown)
- Disease stage III/IV (Yes, No, Unknown)
- Extranodal involvement (Yes, No, Unknown)

2.3.3.5 Prior anti-neoplastic therapies

All prior anti-neoplastic therapies including medications for hematological disease and radiotherapy will be listed.

2.3.3.6 Protocol deviation summaries

A listing of protocol deviations will be produced including the accompanying deviation code. In addition, all COVID-19 related protocol deviations will also be listed.

2.3.4 Unscheduled visits

All data collected at unscheduled visits will be listed.

2.3.5 Others

All other data collected at baseline will be listed.

2.4 Treatments (study treatment, rescue medication, concomitant therapies, compliance)

2.4.1 Tisagenlecleucel re-infusion

Total viable cells re-infused (in cells), total CAR positive viable T-cells re-infused (in cells/kg) and total CAR positive viable T-cells re-infused (in cells) will be listed for each patient using Safety Set.

The approved dose range for this trial is: 0.2 to 5.0×10^6 CAR positive viable T-cells / kg for patients' ≤ 50 kg body weight or 0.1 to 2.5×10^8 (i.e. 10 to 250×10^6) CAR positive viable T-cells for patients > 50 kg body weight. Patients will be categorized as above, within or above the prescribed dose range by body weight stratum (i.e. ≤ 50 kg and > 50 kg).

Note: Body weight refers to the body weight collected on the "Vital Signs" eCRF at the Study Day 1 assessment (i.e. re-infusion assessment).

2.4.2 Additional treatments

Additional treatments data will be listed using the Enrolled Set.

Lymphodepleting chemotherapy received after enrollment but prior to re-infusion with tisagenlecleucel will be listed. Types of lymphodepleting chemotherapies received (fludarabine based lymphodepleting therapy, non-fludarabine based lymphodepleting therapy and no lymphodepleting therapy) will also be listed by patient.

Note: Fludarabine based lymphodepleting chemotherapy refers to fludarabine or fludarabine phosphate.

Any instances of bridging therapy will also be listed.

2.4.3 Prior and concomitant medications and therapies

Prior (pre re-infusion) and concomitant (post re-infusion) medications will be listed by the reported term and PT according to the WHO Drug Reference List dictionary (version 202109 GLOBAL B3 or higher).

Significant non-drug therapies post re-infusion including stem cell transplants (SCTs) will be listed.

The number of patients requiring anti-cytokine medications for the management of Cytokine Release Syndrome (CRS) as well as the dosage will be listed by patient using Enrolled Set.

In addition, all post re-infusion anti-neoplastic therapies including medications for hematological disease and radiotherapy will be listed using Safety Set.

2.5 Subgroups of interest

Not applicable.

2.6 Analysis of the primary objective

The primary objective of the study is to evaluate the efficacy of re-infusion of tisagenlecleucel for restoring B-cell aplasia as measured by the incidence of B-cell aplasia within 12 months following tisagenlecleucel re-infusion.

Where **loss of B-cell aplasia** (i.e. B-cell recovery) is defined as:

- PB absolute B lymphocyte count $\geq 50/\mu\text{L}$, OR
- Peripheral blood B lymphocyte $\geq 10\%$ of the total lymphocytes

And where **B-cell aplasia** is defined as:

- PB absolute B lymphocyte count $< 50/\mu\text{L}$

The primary analysis of the study was to be performed after all patients had completed the 12-month follow-up period or discontinued earlier. However, this study terminated early due a very low rate of enrollment, and only 5 out of a planned 54 patients were enrolled; the low sample size provides insufficient data to perform the planned statistical analyses (see [Section 4](#)). Therefore, the available study data will be listed only for the primary objective using Full Analysis Set.

2.6.1 Primary endpoint

The primary endpoint for this study is defined as the proportion of patients who restore B-cell aplasia (as defined in [Section 2.6](#)) within 12 months following re-infusion with tisagenlecleucel as measured by circulating B-lymphocytes ($< 50/\mu\text{L}$) in PB. B-cell aplasia data will be listed by patient using Full Analysis Set.

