#### **4.5 Risks and benefits**

Appropriate eligibility criteria and specific dose-limiting toxicity definitions, as well as specific dose modification and stopping rules, are included in this protocol. Recommended guidelines for prophylactic or supportive management of tisagenlecleucel induced AEs are provided in [Appendix Table 16-1](#).

The risk to subjects in this trial may be minimized by compliance with the eligibility criteria and study procedures, as well as close clinical monitoring. [Refer to the Kymriah Product Information]

As of 26-Mar-2019, tisagenlecleucel has been administered to over 579 patients in clinical trials across the dose ranges tested, and has a well characterized safety profile in pediatric and young adult patients. Overall, it is anticipated that the benefits of tisagenlecleucel therapy, including complete and long-term remissions when compared to the current standards of care, will outweigh the risks in this study.

Safety risks that have been identified with the use of tisagenlecleucel or are considered potentially associated with tisagenlecleucel are briefly outlined below.

Poor tisagenlecleucel persistence and early loss of B-cell aplasia within 6 months of tisagenlecleucel infusion are associated with higher risk of relapse. Patients with early B-cell recovery usually proceed to other experimental CAR-T cell therapies or allogeneic hematopoietic stem cell transplant (allo-SCT). Allo-SCT is associated with significant morbidity and mortality, particularly in patients who had received prior allo-SCT. Additionally,

subsequent allo-SCT may not be feasible in some patients because of the lack of a suitable donor or ineligibility due to co-morbidities (Crotta 2017).

Reinfusion of one or more additional dose/s of tisagenlecleucel can restore B cell aplasia in some patients with early evidence of poor persistence or B-cell recovery (by extending persistence) and improve durable remission rates (Maude 2016). If successful, patients may not require subsequent therapies and/or allo-SCT.

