#### **Medication restrictions prior to tisagenlecleucel infusion**

1. **Steroids:** Therapeutic doses of steroids must be stopped >72 hours or 5 half-lives, whichever is greater, prior to tisagenlecleucel infusion. However, the following physiological replacement doses of steroids are allowed: <12 mg/m^2/day hydrocortisone or equivalent
2. **Steroids or other immunosuppressant drugs** should NOT be used as pre-medication for tisagenlecleucel therapy (refer to [Section 6.2.1/ Pre-Infusion Evaluation](#)) or following tisagenlecleucel infusion, except as required for physiological glucocorticoid replacement therapy, or under life threatening circumstances. Use of steroids with blood product administration should be avoided just prior to and following tisagenlecleucel if possible or at least minimized.
3. **CNS disease prophylaxis or intrathecal therapy** must be stopped > 1 week prior to tisagenlecleucel infusion (e.g. intrathecal methotrexate)
4. **Radiation therapy** must be stopped > 2 weeks prior to tisagenlecleucel infusion
5. **Investigational therapies** must not be used at any time while on study until the first progression following tisagenlecleucel infusion
6. **Live vaccines** must not be used in tisagenlecleucel recipients for at least 6 weeks prior to lymphodepletion and during tisagenlecleucel treatment until immune recovery
7. **Granulocyte macrophage-colony stimulating factor** has the potential to worsen CRS symptoms and is not recommended during the first 3 weeks after tisagenlecleucel infusion or until CRS has resolved. Short acting granulocyte colony stimulating factor (G-CSF)

should not be given 72 hours prior to tisagenlecleucel infusion and long acting G-CSF should not be given 10 days prior to tisagenlecleucel infusion.

8. **Antiproliferative therapies**, other than lymphodepletion including low dose daily or weekly maintenance chemotherapy) should not be used within 2 weeks prior to infusion.
9. Short acting drugs used to treat primary disease (e.g. hydroxyurea) must be stopped > 72 hours prior to tisagenlecleucel.

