**12.4.1 Definition of primary endpoint(s)**

The primary endpoint for this study is the proportion of patients who restore B-cell aplasia within 12 months following re-infusion with tisagenlecleucel.

B-cell aplasia is defined as:

- PB absolute B lymphocyte count  $< 50/\mu\text{L}$ , AND
- presence of CTL019 cells by qPCR in the peripheral blood

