**12.4.3 Handling of missing values/censoring/discontinuations**

Patients in the study who are of unknown clinical response will be treated as non-responders. Other missing data are simply noted as missing on appropriate tables/listings.

Patients who proceed to HSCT while in remission after tisagenlecleucel re-infusion will be censored at the time of HSCT.

The volume of missing data generated due to the COVID-19 pandemic may also be assessed and sensitivity analyses will be performed, if deemed appropriate.

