#### **12.5.2 Event free survival (EFS)**

EFS is the time from date of tisagenlecleucel re-infusion to the earliest of the following:

- Death from any cause after remission
- Relapse
- Treatment failure: Defined as no response in the study and discontinuation from the study due to any of the following reasons:
  - Death
  - Adverse event (including abnormal laboratory values or abnormal test procedure
  - results)

- Lack of efficacy or progressive disease
- New anticancer therapy

In the main analysis of EFS, patients who proceed to SCT after tisagenlecleucel re-infusion will be censored at the time of SCT. In addition, a sensitivity analysis of EFS will be performed without censoring SCT. EFS will be assessed in all patients in the FAS. The distribution function of EFS will be estimated using the Kaplan Meier (KM) method. The median EFS along with 95% confidence intervals will be presented, if appropriate.

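### Restored B-cell aplasia has no cut-off at later anticancer therapy, another cellular therapy or transplant, so a patient whose re-infusion failed could be read as restored

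*SAP*

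**What the plan says.** **Endpoint.** SAP 2.6 defines B-cell aplasia by the count alone, below 50/µL in peripheral blood. SAP 2.6.1 applies that over 12 months from re-infusion and states that "B-cell aplasia data will be listed by patient using Full Analysis Set". Protocol 12.4.1 had a second condition, "presence of CTL019 cells by qPCR in the peripheral blood", which SAP Section 4 removes.

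**Later therapy.** Protocol 12.4.3 has one rule: "Patients who proceed to HSCT while in remission after tisagenlecleucel re-infusion will be censored at the time of HSCT". It also counts unknown clinical response as non-response. SAP 2.6.3, which would carry such rules, is marked not applicable, as are the supportive and sensitivity analyses in SAP 2.6.4. "New anticancer therapy" appears in protocol 12.5.2 as one of the discontinuation reasons that make a non-responder a treatment failure for EFS. It has no counterpart in the primary endpoint.

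**What is listed.** Under SAP 2.4.3, "all post re-infusion anti-neoplastic therapies including medications for hematological disease and radiotherapy will be listed using Safety Set". No link is made to the aplasia data.

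**Status.** SAP 2.6, 2.6.2 and Section 4 say that 5 of 54 planned patients were enrolled and that the primary data will be listed, not analysed.

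**The concern.** A B-cell count falls for several reasons. Chemotherapy, a B-cell-directed agent, transplant conditioning or a different CD19 CAR-T can each bring it below 50/µL. If such a count falls inside the 12-month window, the SAP definition is met whether or not re-infusion did anything.

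The error runs in one direction, because later therapy can add apparent restorations and cannot remove any. It also falls on the patients for whom re-infusion worked least well, since they are the most likely to be treated again. The aplasia listing is now the whole primary-efficacy record, and protocol 13.3 foresees public posting of results, so a wrongly classified patient would not be diluted by a larger sample.

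**Working it through.** **1. Can such a count arise under the documents?**

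- Protocol 6.2.2 says investigational therapies "must not be used at any time while on study until the first progression following tisagenlecleucel infusion". Its limits on antiproliferative drugs and radiation concern the period before infusion. It sets no limit on standard anticancer therapy after progression.
- Protocol 9.1.1 requires discontinuation for prohibited treatment but does not name new anticancer therapy as such. Patients who discontinue are asked to return for scheduled assessments where possible.
- Protocol Section 8 asks for the final-visit assessments at early exit. In Table 8-1 the final visit includes B-cell flow cytometry. Scheduled post-infusion flow is at D28, M3 and M12.
- The unknown-response rule in 12.4.3 does not apply, because a measured low count is not unknown.

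A patient who relapses after re-infusion, is treated again and has a count below 50/µL at M3 or M12 therefore meets the SAP definition.

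**2. The plan's own design figure.** Inputs from SAP 2.6.2 and Section 3: null rate 0.10, alternative 0.25, one-sided 2.5%, n = 49, rejection at 10 restored.

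- Clopper-Pearson lower limit: 10/49 gives 0.1024, above 0.10; 9/49 gives 0.0876, below it. The threshold of 10 is right.
- P(X ≥ 10 | n = 49, p = 0.10) = 0.0215.
- P(X ≥ 10 | n = 49, p = 0.25) = 0.817.

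The design reproduces.

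**3. Illustration for the abandoned test.** Let c be the share of true failures credited only through a count taken after later therapy. The documents give no value, so c is assumed. With a true restoration rate of 0.10, the credited rate is 0.10 + 0.90c.

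| c (assumed) | credited rate | P(X ≥ 10 of 49) |
|---|---|---|
| 0 | 0.100 | 0.0215 |
| 0.02 | 0.118 | 0.0575 |
| 0.05 | 0.145 | 0.164 |
| 0.10 | 0.190 | 0.457 |
| 0.20 | 0.280 | 0.914 |

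A rule that stops credit at later therapy returns the figure to 0.0215. The planned n does not change.

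**4. The closed trial.** The Full Analysis Set holds at most 5 patients, so one reclassified patient is at least 1/5 = 20 percentage points. SAP 2.6.2 still carries a sentence promising a Clopper-Pearson interval before it says the data will only be listed. If that interval were produced on 5 patients, moving from 2/5 to 3/5 would move the lower limit from 0.053 to 0.147, across the 0.10 benchmark.

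**The case against.** The strongest reply is that no primary result will exist to be biased. The test is dropped, SAP 2.6.1 asks for a listing and specifies no responder flag, and much of what a reader needs is already printed. Study days appear in the relevant listings (SAP 2.1.1.7), later antineoplastic therapies are listed (2.4.3), and qPCR results are listed by subject and visit (2.10). With at most five patients, a careful reader could put the counts and the treatments in order. This stands, and it lowers the severity. It does not supply the missing rule: nothing tells the reader to make that comparison or says which classification prevails.

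Four stronger inferences are tempting, and the documents do not carry them.

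- **That the trial's false-positive rate is 16% or 46%.** Those figures rest on an assumed c. They also join the count-only definition to a test designed under the count-plus-qPCR definition and dropped in the same amendment that removed qPCR. Under the protocol's definition the inflation would be smaller, by an unknown amount.
- **That patients whose re-infusion fails are expected to receive another CAR-T on study.** Protocol 4.5 says "Patients with early B-cell recovery usually proceed to other experimental CAR-T cell therapies or allogeneic hematopoietic stem cell transplant (allo-SCT", but it describes usual practice after early B-cell recovery as background to offering re-infusion. Exclusion 15 bars enrolled subjects from parallel investigational studies. That sits in tension with the until-progression wording of 6.2.2, and the two need reconciling. The route through standard anticancer therapy does not depend on this.
- **That EFS and the primary endpoint contradict each other.** EFS treatment failure requires both no response and discontinuation. Aplasia with an EFS event is not impossible either: in protocol 1.2, a group described mainly by continued aplasia includes one CD19-negative relapse.
- **That every early-exit sample follows new therapy.** Section 8 asks for that visit as soon as possible, so it may come first.

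**Conclusion.** The gap is real. As written, the SAP definition would credit re-infusion with a low count produced by later antineoplastic therapy, another cellular therapy or a transplant. Removing qPCR widened the gap, because a low count without detectable infused cells now qualifies. The protocol's version was narrower, but it too had no rule for later therapy other than transplant in remission, and it did not say what censoring means for a yes/no endpoint.

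The present effect is limited to how at most five patients are classified. The documents do not show that any enrolled patient had such a count, and a reader should not infer that one did. Severity is minor to moderate. It is worth correcting before database lock so that the rule is not chosen after individual results are seen.

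**What to change.** Add to SAP 2.6.1:

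> Only samples taken before the first post-re-infusion antineoplastic therapy, other cellular therapy or HSCT count towards restored B-cell aplasia; a patient with no qualifying sample before that date is not restored.

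Record this in SAP Section 4 as a change from the protocol, since it replaces the censoring rule in 12.4.3. The closed protocol need not be amended.

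In the B-cell aplasia listing, print the start date of that therapy and the same-visit qPCR result beside each count, and flag later samples. Tables 8-1 and 8-5 schedule flow and qPCR at the same visits, so the pairing needs no new samples.

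The cost is one sentence, one derived flag and extra listing columns. Two drawbacks should be stated. The number restored may be slightly lower. Therapy dates may also be incomplete: Table 16-2 collection ends at Month 12 or discontinuation, and after discontinuation new treatments are recorded only if the patient agrees to abbreviated contact (protocol 9.1.1). Where the date was not collected, mark it as unknown so that the reader can see that the order of count and therapy is not established.
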